5.2.4 Sensitivity Analyses

Assessment of the sensitivity or robustness of the findings to the key assumptions is essential in trials. The following sensitivity analyses may be conducted to explore the effects of alternative analysis models, alternative missing data approaches, balancing prognostic imbalance, as-treated analyses, variability in co-interventions, and alternative definitions of SSI.

- Using different analysis models:* There are several methods for analyzing cluster randomized crossover trials.^{51,55} Therefore, our sensitivity analyses will explore alternative multi-level models with different correlation structures for the error.^{52,55}
- Different methods of handling missing data:* There are several methods of handling missing data in trials.⁵⁵ Multiple imputation assumes that the data are missing at random—an assumption that is not verifiable in practice. Other imputation methods will be used such as worst case scenario to impute missing data and assess the robustness of the results.⁵⁶ For

the worst case scenario analysis, we will assume that a random sample of participants lost to follow-up experienced a study event. For this sensitivity analysis, the proportion assumed to experience a study event will be equivalent to the upper confidence interval of the observed pooled event rate for each study outcome.

3. *Adjusted analyses for prognostic imbalance:* We will also perform sensitivity analyses that assume prognostic imbalance between the two treatment groups based on the following key variables known to be risk factors for SSI or reoperation after extremity fracture management: soft tissue injury, time from injury to definitive fixation, age, work-related injury, and employment status.⁵ For patients with open fractures, these additional risk factors will also be considered: Gustilo fracture type, lower extremity fracture, wound contamination, time from injury to first debridement, antiseptic wound dressing in the emergency department, method of fixation, and wound closure at initial debridement.⁵ Adjusted analyses including the above risk factors and treatment group as independent variables will be performed for the SSI and reoperation outcomes.
4. *As-treated analyses:* The proportion of surgical procedures receiving the incorrect, non-allocated antiseptic solution will be reported. “As-treated” sensitivity analyses will be performed using the solution received as the independent variable. For participants that were treated in a single fracture surgery, they will be analyzed using the antiseptic solution received. For participants who received multiple fracture surgeries, two analyses will be performed. First, the antiseptic solution used in their last surgery prior to a study outcome event will define their study treatment. For the second analysis, the antiseptic solution received in the majority of their fracture surgeries will define their study treatment. Participants who were treated with multiple fracture management surgeries, but received equal exposure to both treatment solutions (e.g., one surgery with CHG and one surgery with iodine), will be analyzed within their originally allocated treatment group.
5. *Co-intervention variability:* Selective censoring of one or more clusters and / or treatment periods will be performed to further explore between-cluster and between-period variability identified in the primary and secondary outcome comparisons. These analyses will be used to explore the robustness of the study conclusions in the context of measured practice variations in co-interventions that differ between participating sites and / or evolve over the duration of the study recruitment. Results that are sensitive to the removal of a cluster(s) and / or period(s) will be reported, along with potential clinical hypotheses that are supported by the measured clinical practice variation.
6. *Quantitative pooling of open fracture and closed fracture populations:* We will quantitatively pool the treatment effects from the open and closed fracture populations if the direction of the effect is consistent across the two populations. The rationale for this sensitivity analysis approach is that a consistent direction of effect in the two populations suggests that the populations and mechanism of effect are similar enough to provide a clinically useful estimate of treatment effect if applied to all surgically treated fractures. If the direction of the effect is in opposite directions, for example, CHG appears to be more effective in closed fractures and iodine povacrylex is more effective in open fractures, then no pooling will be performed. This scenario would suggest that the populations and heterogeneity of treatment effect is too divergent; therefore, a pooled treatment estimate

would not be clinically useful since surgeons will continue to view the choice of antiseptic skin solution for open and closed fractures patients as separate treatment decisions.

7. *Exploratory SSI definitions:* The above analyses will be repeated for the primary comparison using the FRI outcome and the CDC definition within 1 year of injury to determine if the study conclusions are sensitive to alternative definitions of SSI.

Table 9 below shows a summary of each potential sensitivity analysis objectives, corresponding outcomes, hypotheses, and methods of analysis.

Table 9: Summary of Sensitivity Analysis Plan

	Objective	Outcome		Hypothesis	Method of Analysis
		Name	Type		
1	Different analysis models	SSI / Reoperation	Binary	Iodine solution will be more effective than CHG solution	Multi-level regression models with different correlation structures
2	Different missing data approach	SSI / Reoperation	Binary	Iodine solution will be more effective than CHG solution	Multi-level regression models with missing data imputed using worst-case scenario
3	Baseline prognostic imbalance	SSI / Reoperation	Binary	Iodine solution will be more effective than CHG solution	Multi-level regression models with prognostic variables & treatment group
4	As-treated analysis	SSI / Reoperation	Binary	Iodine solution will be more effective than CHG solution	Multi-level regression models using “as treated” treatment group
5	Co-intervention variability	SSI / Reoperation	Binary	Cluster- and period-variability is related to co-interventions	Censoring of cluster(s) and/or period(s) with differences in co-interventions
6	Quantitative pooling	SSI / Reoperation	Binary	Iodine solution will be more effective than CHG solution in all fracture patients	Meta-analysis with fixed effects
7	Exploratory SSI definitions	FRI / CDC SSI within 1 year	Binary	Iodine solution will be more effective than CHG solution	Multilevel regression model

Note: CHG = chlorhexidine gluconate; SSI = Surgical Site Infection; FRI = fracture-related infection; CDC = Centers for Disease Control and Prevention

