We have estimated the CHG group will experience a SSI incidence of 12.5% in the open fracture population and a 3.5% incidence within the closed fracture population.^{3,4} Compared to CHG, we have assumed the iodine povacrylex solution will achieve a 0.65 risk reduction for SSI and unplanned fracture-related reoperation in each fracture population.²² This effect was selected as the smallest difference that would be important to detect, in the sense that any smaller effect would not be of clinical or substantive importance. Additionally, this effect was deemed more conservative than data reported by Swenson et al. and was consistent with feasible recruitment goals.²¹

We have based our sample size assumptions using a single crossover, 2-period design to ensure the most conservative sample size estimate. Recent simulation data suggest that increasing the number of period crossovers can increase the statistical power of a given sample size.⁴⁶ The initial power estimate assumed 10 recruiting clusters, a 10% loss to follow-up rate,⁴ and applying the between-cluster variance of 0.095 observed in the FLOW trial. Based on enrollment of a minimum of 1,540 open fracture patients and 6,280 closed lower extremity and pelvic fractures, greater than 80% power would be achieved for each fracture population. Subsequent to the initial power calculations, the early trial experience demonstrated a need to increase the number of clusters to obtain a feasible recruitment pace. As a result, a minimum 18 clusters will enroll participants into PREPARE. The increase in clusters results in a marginal increase in power (~2%).

Table 5 and **Table 6** below outlines the summary of the initial sample size assumptions. These sample size estimates are rounded up to the nearest multiple of 20 to ensure balance among 10 clinical sites and two interventions.

Table 5: Sample Size Assumptions for Open Fractures

Baseline SSI Risk	Iodine Risk Ratio	Iodine Odds Ratio	Sample Size	Sample Size Increased by 10%
-------------------	-------------------	-------------------	-------------	------------------------------

10.0%	0.62	0.59	1,600	1,760
10.0%	0.65	0.63	1,960	2,100
10.0%	0.67	0.65	2,200	2,420
10.0%	0.70	0.68	2,600	2,860
12.5%	0.62	0.59	1,300	1,440
12.5%	0.65	0.62	1,400	1,540
12.5%	0.67	0.64	1,600	1,760
12.5%	0.70	0.67	1,800	1,980
14.0%	0.62	0.58	1,200	1,320
14.0%	0.65	0.61	1,300	1,440
14.0%	0.67	0.64	1,500	1,660
14.0%	0.70	0.67	1,800	1,980

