5.2 Statistical Methods

5.2.1 Analysis Plan Overview

A detailed statistical analysis plan will be published prior to the completion of the trial. The following analysis plan will be conducted independently for the open and closed fracture populations. For each population, the analyses and reporting of the results will follow the CONSORT guidelines for reporting of both pragmatic trials⁴⁷ and cluster-randomized trials.⁴⁸ The process of participant enrollment and flow throughout the study will be summarized using a flow-diagram. Participant demographics and baseline outcome variables will be summarized using descriptive summary measures expressed as mean (standard deviation) or median (interquartile range) for continuous variables depending on the distribution, and number (percent) for categorical variables.⁴⁹ An ITT principle will be adopted to analyze all outcomes and the unit of analysis will be the individual participants. Missing data will be assumed to be missing at random and will be handled with multiple imputation.^{50,51}

The primary analysis will compare the treatment groups using the SSI outcome and the secondary analysis will compare the unplanned fracture-related reoperation outcome. The secondary comparison will be conducted in accordance with best practice guidelines for secondary analyses. For all models, the results will be expressed as relative measure of effect (odds, risk, or hazard ratios) and corresponding two-sided 95% confidence intervals.

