28 All study outcomes will be tested for superiority.

29

30 **2.5 Interim Analysis and Stopping Guidance**

31 PREPARE Closed does not have a planned interim analysis. However, the trial's Data and Safety  
32 Monitoring Committee reviews the reporting of serious adverse events biannually and can  
33 recommend early stopping if safety concerns are identified.

34

35 **2.6 Timing of Outcome Assessments**

36 Research personnel will contact study participants at 6 weeks, 3 months, 6 months, 9 months, and  
37 12 months after their fracture. Our primary outcome will be surgical site infection (SSI) and it will  
38 be assessed at 30 days (superficial infections) and at 90 days (deep and organ space infections)  
39 after definitive fracture management surgery. The secondary outcome will be occurrence of an  
40 unplanned fracture-related reoperation within 12 months of the fracture. Additional time points  
41 will be used for our planned sensitivity analyses.

42

43

44

45 **3.0 STATISTICAL PRINCIPLES**

46 **3.1 Confidence Intervals and P-Values**

47 All statistical tests will be two-sided and performed using a 5% significance level. We will report  
48 all confidence intervals as 95% and two-sided. All results will be expressed as odds ratios produced  
49 by analyses described in section 5.2. Interaction p-values will be provided for the subgroup  
50 analyses. We will not adjust for multiple testing, and all sensitivity analyses and secondary results  
51 will be interpreted as exploratory.

52

53 **3.2 Adherence and Protocol Deviations**

54 Adherence will be assessed at the definitive fracture surgery for each participant and will be binary  
55 in its definition. We will report adherence as the number and percentage of participants who  
56 received the allocated intervention at their definitive fracture management surgery. If the  
57 participant has multiple closed fractures and received the non-allocated treatment at the definitive  
58 fracture management surgery for any of their closed fractures, we will consider them non-adherent.  
59 We will also tabulate the reasons for non-adherence. The adherence percentages and reasons for  
60 non-adherence will be reported by treatment arm.

61

62 Our rationale for defining adherence based solely on the antiseptic solution used during the  
63 definitive fracture management surgery is that the vast majority of closed fractures do not require  

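### Protocol 5.2.4 item 6 pools open and closed effects only when their observed directions agree, so under no effect a reported pooled 95% CI covers about 90%; a minor point, because the analysis is optional and in neither SAP

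*Protocol*

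**What the plan says.** Item 6 of Protocol 5.2.4 says the trial will "quantitatively pool the treatment effects from the open and closed fracture populations if the direction of the effect is consistent across the two populations". If the directions are opposite, "then no pooling will be performed". Row 6 of Table 9 gives the method as "Meta-analysis with fixed effects", for SSI and for reoperation, under the hypothesis that iodine is better across all fracture patients. The stated rationale is that a shared direction shows the populations and mechanism to be alike enough for one estimate to guide care of all surgically treated fractures.

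The error and confidence levels are the ordinary ones. SAP section 3.1 (the same in the Closed and Open plans) says "All statistical tests will be two-sided and performed using a 5% significance level", and Protocol 5.2.1 attaches "corresponding two-sided 95% confidence intervals" to the results of all models. No text adjusts the pooled analysis for the condition on direction.

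The status of the analysis is weak. Protocol 5.2.4 introduces its sensitivity analyses as ones that may be done, and Protocol 5.2.2 defers the final methods to a separate SAP. Section 5.4 of each SAP lists four sensitivity approaches: alternative SSI definitions, as-treated, complete-case and Bayesian. Pooling is not among them, and neither SAP says that it was dropped, although both explain their change to the as-treated definition. SAP 3.1 treats all sensitivity results as exploratory.

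**The concern.** The rule uses the two observed estimates to decide whether a pooled estimate will exist, then analyses it as if no such decision had been made. When the true effects are near zero, requiring equal signs discards the trials in which the two estimates cancel. The pooled estimates that remain lie too far from 1, and the standard interval is too narrow for them.

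The rule also does not do the job given to it. Two estimates fall on the same side of 1 half the time by chance alone, so agreement says little about similarity. Conversely, two estimates that straddle 1 by chance would be read as divergence. The size of the difference between the populations, with its uncertainty, is what bears on whether to combine them, and item 6 does not ask for it.

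At stake is the calibration of one supplementary estimate and interval when the true effect is null or small. The Protocol's own earlier fracture evidence (section 1.5, adjusted hazard ratio 0.88, 95% CI 0.69 to 1.12) lies in that small-effect range.

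**Working it through.** **Inputs.** Protocol 5.1 assumes "SSI incidence of 12.5% in the open fracture population and a 3.5% incidence within the closed fracture population" on CHG, a "minimum of 1,540 open fracture patients and 6,280 closed lower extremity and pelvic fractures", and "a 10% loss to follow-up rate". Analysed per arm: open 1,540 × 0.9 / 2 = 693; closed 6,280 × 0.9 / 2 = 2,826. The two estimates are taken as independent: no participant is in both populations (Protocol 4.2), and the planning assumes zero between-period variance (notes to Tables 5 and 6).

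**Standard errors and weight under no effect.** SE(log OR) = √[2 / (n p (1 − p))].
- Open: 693 × 0.125 × 0.875 = 75.80, so SE = √(2 / 75.80) = 0.162.
- Closed: 2,826 × 0.035 × 0.965 = 95.45, so SE = √(2 / 95.45) = 0.145.
- Inverse-variance weight of open: w = 75.80 / (75.80 + 95.45) = 0.443.

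**The plan's nominal figure, without the sign condition.** Z = √w · z_open + √(1 − w) · z_closed, with independent standard normal z's, is itself standard normal. Pooling always therefore gives 5.0% rejection and 95.0% coverage.

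**With the sign condition, no effect.**
- P(signs agree) = 0.50.
- P(signs agree and |Z| > 1.96) = 2 ∫₀^∞ φ(x) [1 − Φ(max{0, (1.96 − √w x) / √(1 − w)})] dx = 0.0486.
- Rejection given that a pooled result is reported: 0.0486 / 0.50 = 9.7%.
- Coverage given reporting: 100 − 9.7 = 90.3%.

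A simulation with 10 clusters, 2 periods and between-cluster variance 0.095 gave 9.9%. Exact ties at OR 1 lower the chance of agreement there to 0.475.

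**Other true effects.** 4,000,000 normal draws each. The CHG arm keeps its planning rate, the iodine rate follows from the OR, and SE = √[1/(n p₀(1 − p₀)) + 1/(n p₁(1 − p₁))]. Coverage is of the precision-weighted average log OR.

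| True OR open / closed | Pooled result reported | Coverage given reporting | Mean reported pooled OR (target) |
|---|---|---|---|
| 1.00 / 1.00 | 50% | 90.3% | 1.00 (1.00) |
| 0.88 / 0.88 | 67% | 93.5% | 0.846 (0.88) |
| 0.85 / 0.85 | 74% | 94.6% | 0.821 (0.85) |
| 0.62 / 0.64 (design) | 99.3% | 95.4% | 0.630 (0.631) |

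**Agreement as a test of similarity.** Suppose iodine works only in open fractures, so the closed OR is 1. The closed estimate then falls on either side of 1 with probability ½. If the open estimate is below 1 with probability q, P(agree) = ½q + ½(1 − q) = ½ for any q. With ORs 0.64 and 1.00, half of trials pool and 60% of those are significant.

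**Sensitivity of the 9.7%.** The reoperation rates for each population are not given, so the weight there is an assumption: for w from 0.2 to 0.5 the figure runs from 8.8% to 9.75%. If shared clusters, periods and allocation correlate the two estimates, an assumed correlation of 0.05 to 0.20 gives 10.6% to 12.9% (w = 0.45). Part of that rise comes from ignoring the correlation, not from the sign rule.

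**The case against.** The strongest reply is that this analysis barely exists in the current plan. It is optional in the Protocol, missing from both SAPs and exploratory by declaration. The two populations are compared separately, so no primary conclusion depends on it. All of that stands, and it sets the importance of the point.

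A reader might infer from the 9.7% that the trial's type I error is inflated. It is not. The chance that the trial reports a falsely significant pooled result is 4.9%; the 9.7% is that figure divided by the 50% chance of pooling. Nor does the rule favour iodine: under no effect the mean reported pooled OR is 1.00, and what is exaggerated is distance from 1 in either direction.

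A reader might also suppose that the pooled figure will be seen alone. Protocol 7.6 commits to submitting each population's results whatever their significance, so both component results should be available.

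Worse-looking cases can be built. With ORs of 0.64 (open) and 1.20 (closed), conditional coverage is 78%. But the rule then withholds pooling in 90% of trials, a significant pooled result appears in only about 4.5% of all trials, and the coverage refers to a weighted average OR of about 0.95 that the documents never name as a target.

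The Protocol's clinical reason for not showing a pooled figure when directions oppose is a fair consideration. It does not make the interval valid when the figure is shown, and sign agreement does not supply the similarity that the rationale relies on.

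**Conclusion.** The point holds as a minor one. Under no effect, a pooled result reported under item 6 carries about 9.7% rejection and about 90% coverage in place of 5% and 95%, while the unconditional false-positive rate stays at about 4.9%. The distortion shrinks as a common effect grows: coverage is 93.5% at OR 0.88, and nothing material remains at the design effect. Agreement of direction is no evidence that the populations respond alike.

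These figures rest on the planning rates and sample sizes, normal approximations and independent open and closed estimates. The documents do not support a claim that the primary results or the trial-wide error rate are affected.

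**What to change.** State in the Protocol and both SAPs whether item 6 is still planned.

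- **If not,** delete item 6 and row 6 of Table 9.
- **If so,** remove the sign condition and report the fixed-effect pooled OR whatever the directions. Beside it give the two population ORs and their ratio (the treatment-by-population interaction) with a 95% CI, and make these the basis for judging whether the pooled figure is of clinical use. State the independence assumption.

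The ratio needs only the two fitted models: log ratio = log OR_open − log OR_closed, with SE √(SE_open² + SE_closed²). Under no effect that is √(0.162² + 0.145²) = 0.22, so the 95% CI runs a factor of about exp(1.96 × 0.22) = 1.5 either side of the estimate. Even this direct comparison is imprecise.

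A joint model of both populations is not needed and would be awkward: the SAPs adjust for different covariates, and some sites may enrol only one cohort (Protocol 4.4.1).

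The cost is a few lines of text and no new data. The small downside is that a pooled figure appears even when the directions oppose, but next to the heterogeneity estimate.

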5.2.5 Interim Analysis

No formal interim analyses are planned and the trial will not be stopped early for benefit. The Data and Safety Monitoring Committee (see Section 7.5.6) will review frequent safety reports and will collectively make judgments on the strength of evidence and the absolute magnitude and seriousness of any safety signals.⁵⁷ The Data and Safety Monitoring Committee may make recommendations regarding the trial.

6.0 DATA MANAGEMENT

6.1 Case Report Forms and Data Transmission

Clinical sites will be provided with the trial CRFs prior to initiation of enrollment. Research personnel at each clinical site will submit the required data, as detailed on the CRFs, to the Methods Center using the REDCap Cloud electronic data capture system. Clinical site personnel will receive a unique login and password for the REDCap Cloud system and will be able to view and modify data for participants recruited at their clinical site.

6.2 Data Integrity

The REDCap Cloud system uses a variety of mechanisms for checking data at the time of entry including skip logic, range checks, and data type checks. Upon receipt of new data, the personnel at the Methods Center will query all missing, implausible, or inconsistent data. Clinical site personnel will be able to review all open queries in the system and will be required to respond promptly.

7.0 ETHICS AND DISSEMINATION

7.1 Research Ethics Approval

The McMaster University Methods Center and all participating clinical sites will receive REB or IRB approval prior to commencing participant enrollment. A central IRB and local IRBs/REBs will be used based on clinical site logistics. Prior to local commencement of the study, each clinical site will provide the Methods Center with a copy of their ethics approval.

